Impact of Behavioral Treatment of Insomnia on Nighttime Urine Production

University of Pittsburgh STUDY19110063

NCT03883724

INTRODUCTION

Nocturnal polyuria (NP) has long been known to be a major contributor to nocturia in the elderly. NP has a strong bidirectional relation with poor sleep especially in the elderly; however, to the best of our knowledge, an intervention directed solely at sleep has never been tried for NP. Our previous studies have shown that improving sleep with BBTI improves nocturia. However, we do not know the mechanisms by which behavioral sleep treatments improve nocturia. The proposed study will be the first to directly examine two plausible mediators: first uninterrupted sleep period (FUSP) and NP. The knowledge gained from this study can help identify 1) impact of sleep intervention on nighttime urine production, and 2) mechanisms by which sleep intervention improves nocturia

STUDY OVERVIEW

This pilot study will provide critical preliminary data regarding the relation between sleep and nighttime urine production in seniors by: 1) examining the impact of behavioral sleep treatment (BBTI- brief behavioral treatment of insomnia) on nighttime urine production- NP and 2) exploring the potential mechanisms by which BBTI impacts nocturia. To address the proposed aims we will perform a randomized controlled pilot trial of 60 healthy community-dwelling men and women aged 65 and over with nocturia and NP. The participants will be randomized to receive the 4-week behavioral sleep intervention BBTI by a trained therapist or an information control intervention. The participants will undergo detailed sleep and bladder assessments pre- and post-intervention to assess the effect of treatment. Data from this study will provide feasibility and pilot data for a subsequent, larger, and more definitive trial.

Outcome measures:

- 1) Change in NP- measured by NPi- nocturnal polyuria index=(nocturnal urine volume/24-hour volume)*100
- 2) Change in nocturia frequency
- 3) Change in FUSP or duration of uninterrupted sleep before the first awakening to void

STUDY FLOW /STUDY PROTOCOL

Study Flow Chart					Post-intervention assessment		
Screening		Baseline assessment		Intervention			
		Visit 1	In-home Assessments	BBTI			
				Session			
Telephone Screening		Apnea Link Plus®	Detailed history & physical	Wk 1	Wk 1 Sleep/ Bladder diary Z-machine ISI		
				Tele call	Tele call		
		IC	Sleep/ Bladder diary Z-machine ISI	Wk 2	Wk 2 Tele call		
				Wk 3	Wk 3 Tele call		
				Wk 4	Wk 4 Tele call		

Screening

Screening procedures include: a) telephone interview and b) Visit 1 to study research suite - Continence Research Unit at UPMC Montefore Hospital. If the subject is interested and qualifies, then the other visits are scheduled.

Telephone Interview

Use IRB approved telephone script to determine eligibility (5-20mins; study nurse/coordinator) ApneaLink mailed to participants who screened eligible upon telephone interview

Visit 1

2 hour; study nurse; in-person

1. Obtain informed consent and sign document.
2. Questionnaires:
 - Medical and Surgical history
 - Current medication
 - Current incontinence
 - ISI
 - MoCA (paper)
3. Uroflow and dip (at appropriate bladder fullness)
4. Measure flow rate and volume of normal void
5. Post-void residual measurement by ultrasound
6. Physical examination: Short physical examination.
7. Sleep/ bladder diary: Explain 3 day sleep and voiding diary instructions.
8. Zmachine: watch instruction video. The device to be worn on the 3rd night of voiding diary
9. Schedule visit 2 with enough time to complete diary.

Visit 2

Randomization

1. Follow study procedure according to the group randomized to.

Telephone follow-up

Week 2 after the visit 2- both groups (BBTI and Control)

Week 4 after the visit 2- both groups

Visit 3

For participants randomized to BBTI group

Post intervention

4 weeks post visit 2

1. Sleep/ Bladder diary (send in mail)
2. Zmachine (send in mail)
3. ISI- completed telephonically.

Inclusion/exclusion criteria

For this study researchers shall enroll: ambulatory and functionally-independent community-dwelling men and women aged 65+ years, with nocturia ≥ 2 /night.

Exclusion criteria:

- Unstable or acute medical or central nervous system conditions
- Untreated, current, severe psychiatric condition
- Untreated, current, severe overactive bladder syndrome
- Post void residual $> 30\text{ml}$
- Sleep apnea with $\text{AHI} \geq 15$
- Currently diagnosed and/or treated Obstructive Sleep Apnea, Restless Legs Syndrome, parasomnia
- CHF, by exam or NT-proB natriuretic peptide (NT-proBNP) $> 30 \text{ pmol/L}$
- Chronic kidney disease, stage III-V (eGFR < 60)
- > 14 alcohol drinks per week
- > 3 caffeinated drinks ($\sim 300\text{mg}$) per day

Statistical Analysis Plan

Randomization: After all baseline assessments are complete, researchers will randomize the participants in to the intervention groups in a 1:1 ratio, with random block sizes chosen from small even numbers, stratified by severity of baseline nocturia (≤ 3 or > 3 /night). To prevent educated guessing, the study statistician will reveal exact details of blocking strategy only at study completion.

Data Analysis: In addition to statistical significance, researchers will employ descriptive statistics and graphical techniques to draw conclusions. Specifically, as appropriate for a pilot study, researchers will focus interpretations on magnitudes of effects from standard statistical methods rather than their p-values, and apply graphical techniques such as needle plots to represent data at the individual level rather than based on averages. Researchers will use SAS® version 9.3 (SAS Institute, Inc., Cary, North Carolina) software, intention-to-treat philosophy, and multiple imputation for missing data in all inferential analyses.

First, researchers will compare baseline characteristics between the group using independent samples t-, Wilcoxon rank sum, chi-square and Fisher's exact tests, as appropriate. Any significant differences will be used as additional covariates in sensitivity analyses. Second, researchers will fit a series of analysis of covariance (ANCOVA) models with pre- to post-intervention change in each outcome as the dependent variable, intervention group as the independent factor of interest, and baseline value of outcome as a covariate. Magnitude and significance of intervention group term will serve as evidence for Aim 1 efficacy hypotheses. Third, for Aim 2, researchers will begin by exploring correlations of pre- to post-intervention changes in nocturia with those in FUSP and NPI. In keeping with Baron and Kenny's framework for mediation analysis, researchers will add FUSP change and NPI change (both individually and together) as additional independent variables to the Aim 1 ANOVA models. Any subsequent reduction in intervention effect will be interpreted as supporting the Aim 2 mediation hypotheses. Statistical significance of the extent of mediation will be obtained using %SOBEL, %INDIRECT and %MEDIATE SAS® macros, as appropriate.

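### Does the visit schedule leave the control arm without any post-intervention outcome data?

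*Combined protocol and SAP*

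**What the plan says.** The Study Overview sets out a "randomized controlled pilot trial of 60 healthy community-dwelling men and women aged 65 and over with nocturia and NP". Participants receive BBTI "by a trained therapist or an information control intervention". The next sentence reads: "The participants will undergo detailed sleep and bladder assessments pre- and post-intervention to assess the effect of treatment". The three outcomes listed there (NPi, nocturia frequency and FUSP) are all changes.

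After Visit 2, the Study Flow / Study Protocol section lists telephone follow-up at weeks 2 and 4, each marked for both arms; the second entry is "Week 4 after the visit 2- both groups". Then come, on separate lines, Visit 3, the label "For participants randomized to BBTI group", a line reading Post intervention, the timing "4 weeks post visit 2", and a numbered list: the diary and the Zmachine, both by mail, and the ISI by telephone.

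Under Randomization, the Statistical Analysis Plan states that "researchers will randomize the participants in to the intervention groups in a 1:1 ratio". Under Data Analysis, the Aim 1 model is an ANCOVA with "pre- to post-intervention change in each outcome as the dependent variable", intervention group as the factor of interest and the baseline value as covariate. Missing data are to be multiply imputed under intention to treat.

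**The concern.** The last group label before the outcome list is for BBTI only, and Visit 3 has no other content. The two telephone contacts just above are marked for both arms, so a reader may take the absence of that marking here as deliberate. On that reading, only BBTI participants would be sent the follow-up diary and device and called for the ISI.

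The stakes would be high. Every outcome is a change from baseline compared between arms. Without control follow-up, Aim 1 has no comparator, Aim 2 (which adds mediators to the same models) fails with it, and the trial becomes an uncontrolled before-after study.

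**Working it through.** The plan gives no figure on this point to reproduce. The check has two parts: what the literal reading would do to the analysis, and which reading the documents support.

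**Inputs.** Total sample 60 (Study Overview); allocation 1:1 (Randomization). The arm size is derived, not stated: 60 × 1/2 = 30.

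**Part 1: estimability.** The Aim 1 model for participant *i* is

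change_i = b0 + b1 × group_i + b2 × baseline_i + error_i,

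with group = 1 for BBTI and 0 for control. The design matrix has three columns: intercept, group and baseline.

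- *Only BBTI assessed.* Observed change scores: 30 of 60, or 50%, all in one arm. Group equals 1 in every observed row, so its column duplicates the intercept. The rank is 2 of 3. Only the sum b0 + b1 can be estimated; b1, the intervention effect, cannot.
- *Multiple imputation in that case.* The imputation model would have no observed control outcome to learn from. Imputed control values would reflect only an assumption about how controls differ from BBTI participants, and the estimated effect would return that assumption.
- *Both arms assessed.* About 30 + 30 change scores. The rank is 3 of 3 and b1 is estimable.

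So the literal reading would be fatal to the comparison, and the alternative costs nothing. Everything turns on which reading the plan supports.

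**Part 2: the places side by side.**

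1. *Study Overview.* The sentence on assessment before and after the intervention directly follows the one describing both arms. Its subject is the participants, with no restriction.
2. *Data Analysis.* A change score with group as a factor presupposes follow-up values in both arms.
3. *Layout of the schedule.* Post intervention stands on a line of its own, as Visit 1, Visit 2, Telephone follow-up and Visit 3 do, and has its own timing and numbered list. Read as a heading, it carries no arm restriction. Heading levels are not preserved in the text available, so layout alone cannot settle this.
4. *Mode of assessment.* All three items are done by mail or telephone. None needs a visit, which fits a separate remote assessment better than the content of Visit 3.
5. *Empty Visit 3.* Visit 2 is almost as bare: apart from randomization, it only tells staff to follow the procedure for the allocated group. The schedule does not spell out intervention content, so a BBTI-only visit without a list is in keeping with its style.
6. *Week 4 contact.* Controls are telephoned at week 4 after Visit 2, the same time point as the follow-up block. This does not prove that they complete the diary, but it is compatible with assessing both arms.
7. *Flow chart.* It has a post-intervention assessment column, but the table is broken in the available text and its rows cannot be tied to arms. It counts for neither reading.

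Items 1 and 2 require follow-up in both arms; items 3 to 6 are consistent with it. Against them stands one label whose scope is unclear.

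**The case for a change.** The strongest opposing case is that staff work from the visit schedule and do not infer procedures from the analysis plan. Group labels are used with apparent care in that section, and the one nearest the outcome list excludes controls. Nor does either reading leave the schedule complete. If the list belongs to Visit 3, controls are omitted; if it is separate, Visit 3 has neither procedures nor timing and the outcome block has no group label. Restoring the heading levels would not supply those missing words. Since a misreading would cost the whole randomized comparison and one line would prevent it, the line should be required.

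Part of this stands. The wording is ambiguous, no line in the schedule expressly assigns the follow-up measures to controls, and the consequence of omitting them is correctly described. What does not stand is the step from an unclear label to uncollected data. That step needs the team to set one label above an explicit statement in the overview and above the whole purpose of the analysis. Nothing in the documents suggests that anyone chose not to assess controls. A label for both arms would be harmless editing, but it would only confirm what the overview already says.

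**Conclusion.** The concern does not hold as a fault in the plan. Taken as a whole, the document provides for post-intervention assessment in both arms, and the ANCOVA can be fitted as specified.

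On that reading the effect is nil: about 30 change scores per arm are still sought, the design matrix has full rank, and no estimate, sample size or procedure changes. The loss of 30 of 60 change scores, all in the control arm, arises only if one label is followed against the rest of the plan.

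This conclusion assumes that the participants in the overview sentence means both arms, as its position implies, and that Post intervention is a separate heading or at least not limited by the Visit 3 label. The available text cannot prove the second point. An intact flow chart showing no control follow-up would reverse the conclusion; nothing in the documents points that way. What remains is a clerical ambiguity that the study team would resolve sensibly.

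### The NPi and FUSP ANCOVAs leave out the nocturia stratum used in randomisation, so their standard errors are too large if the stratum predicts change

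*Combined protocol and SAP*

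**What the plan says.** Under Randomization, the Statistical Analysis Plan allocates participants "in a 1:1 ratio, with random block sizes chosen from small even numbers", "stratified by severity of baseline nocturia (≤ 3 or > 3 /night").

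Under Data Analysis, it fits one ANCOVA of pre-to-post change per outcome, with "intervention group as the independent factor of interest, and baseline value of outcome as a covariate". It then states: "Magnitude and significance of intervention group term will serve as evidence for Aim 1 efficacy hypotheses". It also says that, because this is a pilot, "researchers will focus interpretations on magnitudes of effects from standard statistical methods rather than their p-values".

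The outcome measures in the Study Overview are NPi, nocturia frequency and FUSP. The first is "Change in NP- measured by NPi- nocturnal polyuria index", a ratio of urine volumes. FUSP is a duration. Neither baseline is the nocturia count from which the strata are cut.

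Other covariates can enter by one route only, after baseline tests between the arms: "Any significant differences will be used as additional covariates in sensitivity analyses". No text adds the stratum, or baseline nocturia, to the NPi or FUSP models.

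**The concern.** Stratified allocation makes the arms nearly equal in nocturia severity, so the treatment estimate no longer varies through chance imbalance in severity. A model without severity does not register this. It leaves the variance due to severity in the residual and reports a standard error as if the arms could have differed in severity. If severity predicts change in NPi or FUSP beyond the outcome's own baseline, the interval is too wide, the test rejects less often than its nominal level, and power is lost.

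The nocturia model, and its Aim 2 extensions with FUSP and NPi change added, are essentially unaffected, because continuous baseline nocturia is already a covariate. Any Aim 2 model of NPi or FUSP change on group, built like the Aim 1 models, would share the gap.

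The sensitivity analyses do not close it. Choosing covariates by baseline significance selects on chance imbalance, and a factor balanced by design is the one least likely to be chosen. The rule has a wider weakness too: a strongly prognostic variable stays out unless it happens to be imbalanced.

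**Working it through.** The plan gives no standard deviation, effect size, alpha or power, so there is no stated figure to reproduce.

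**Inputs from the documents:** 60 participants (Study Overview); 1:1 allocation in small even blocks within two nocturia strata; ANCOVA on group and own baseline.

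**Assumptions:** 40% of participants in the upper stratum; a treatment effect of 0.6 residual SD; a two-sided 5% test. The share *s* of the residual variance (after own baseline) that the stratum explains is not in the documents, so it is varied from 0 to 30%.

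**Formulas,** with the planned model's residual SD set to 1 and exact balance within strata:

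- Planned SE ≈ √(4/60) = 0.258. With t(57) = 2.00 the 95% half-width is about 0.52 SD, whatever *s* is.
- SE with the stratum ≈ 0.258 × √(1 − s), which is also the true SD of the planned estimate.
- SE ratio, planned to adjusted, ≈ 1/√(1 − s). For s = 0.10 it is 1/√0.90 = 1.054; for s = 0.30 it is 1/√0.70 = 1.195.
- Type I error as planned ≈ P(|t| > 2.00/√(1 − s)). For s = 0.30 the cut-off is 2.39, giving about 2.0%.

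**Simulation** (20,000 trials per setting, n = 60, exact balance within strata):

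| Stratum share of residual variance | SE ratio, planned/with stratum | 95% half-width with stratum (planned about 0.52 SD) | Type I error as planned | Power as planned | Power with stratum |
|---|---|---|---|---|---|
| 0% | 1.00 | 0.52 | 4.8% | 62% | 62% |
| 2% | 1.01 | 0.51 | 4.8% | 62% | 63% |
| 5% | 1.03 | 0.51 | 4.2% | 62% | 64% |
| 10% | 1.06 | 0.49 | 4.0% | 63% | 67% |
| 20% | 1.12 | 0.46 | 3.0% | 63% | 71% |
| 30% | 1.20 | 0.43 | 1.8% | 64% | 77% |

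The mean estimate was 0.60 in both models, so there is no bias. Blocks of 2, 4 and 6, which can end incomplete, gave the same pattern: ratios 1.00/1.01/1.03/1.05/1.12/1.20 and type I error falling from 4.5% to about 2%.

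**Independent check on another scale.** Here the stratum effect is fixed in SDs (half the sample in each stratum, stratum-baseline correlation 0.3, blocks of 2, 4 and 6, 12,000 trials). For effects of 0, 0.5, 1.0 and 1.5 SD, the planned SE was 1.00, 1.02, 1.09 and 1.19 times the estimate's true SD, with type I error of 4.9, 4.6, 3.2 and 1.9%. With the stratum added, it was 4.9-5.1%. As a control, the 1.0 SD case with blocks that ignored the strata gave a ratio of 1.00 and 4.9%. The conservatism therefore comes from stratifying and then omitting the factor.

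**How far the upper rows can be trusted.** A normal variable cut at its top 40% keeps φ(z)²/[p(1 − p)] = 0.386²/0.24 = 0.62 of its explained variance. For the stratum to explain 20-30%, continuous nocturia would have to explain 0.20/0.62 = 32% to 0.30/0.62 = 48% of what own baseline leaves. These rows are an upper end.

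**Nocturia model.** Adding the indicator for more than 3 per night to continuous baseline nocturia gave an SE ratio of 0.994, so there is no gain.

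**Baseline tests.** Each variable, prognostic or not, is selected with about 5% probability. The plan does not say how many are tested. With 4 independent variables, the chance of at least one selection is 1 − 0.95⁴ = 19%; with 10, 1 − 0.95¹⁰ = 40%. At pairwise correlation 0.5 these become 16% and 29%. Under stratified blocks, the stratum itself was selected in 0 of 8,000 simulated trials in every setting.

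**The case against.** The strongest reply is that the quantity the plan puts first, the size of the effect, is barely touched. Stratified allocation has already delivered the precision. In a block simulation with a 0.6 SD effect, the true SD of the estimate, planned against adjusted, was 0.248 and 0.247 at a 10% share, 0.236 and 0.235 at 20%, and 0.221 and 0.219 at 30%. Only the reported error changes, and the plan does not mention confidence intervals. This is correct and limits the stakes. It does not remove the point, because the plan also takes the significance of the group term as Aim 1 evidence, and an effect size is hard to read without an honest standard error.

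Second, the association is unknown, and at low shares the gain is slight. That stands. It may also be smaller where the outcome's baseline overlaps with nocturia, as FUSP's may. For a fixed 1.0 SD stratum effect, the ratio of planned SE to true SD falls from 1.10 at zero stratum-baseline correlation to 1.04 at 0.6.

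Third, the plan writes out no separate mediator models for NPi or FUSP. The Aim 2 part is therefore conditional on such models being fitted.

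Fourth, baseline testing is a separate matter, confined to sensitivity analyses. It adds no weight to the main point.

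**Conclusion.** The concern holds, and its impact is minor. The NPi and FUSP models omit the factor that randomisation was stratified on. If that factor predicts change beyond own baseline, their standard errors are conservative. There is no bias and no excess of false positives.

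The size depends on an association the documents do not report. Under the assumptions above it runs from nothing, through 1-2 points of power at a 2-5% share and 4 points at 10%, to 8-13 points at 20-30%. Changing the upper-stratum share to 20% or 50% moved the SE ratios by at most about 0.002. The Introduction treats nocturnal polyuria as a contributor to nocturia, which makes some association plausible. It does not show prediction beyond own baseline.

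The change should be made because it costs almost nothing, not because the planned analysis is invalid.

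**What to change.** 1. Add the stratification factor (at most 3, or more than 3, per night) to the ANCOVAs for change in NPi and change in FUSP, and to any Aim 2 model with NPi or FUSP change as the dependent variable. Continuous baseline nocturia would also serve, but one form should be named in advance; the factor actually used in randomisation is the natural choice. The nocturia model needs no change.
2. For the sensitivity analyses, replace selection by baseline test with a short covariate list, fixed in advance from data already collected and justified as prognostic by the investigators. Report baseline characteristics descriptively.

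The cost is SAP wording and one degree of freedom in each NPi and FUSP model, with no new data. If the stratum explains nothing, the loss is negligible: in the independent check the mean SE was 0.2597 with the stratum and 0.2593 without.

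### Does adding FUSP change and NPi change to the nocturia model without their baseline values undermine the Aim 2 mediation analysis?

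*Combined protocol and SAP*

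**What the plan says.** The relevant text is in the Data Analysis part of the Statistical Analysis Plan. Aim 1 uses "analysis of covariance (ANCOVA) models with pre- to post-intervention change in each outcome as the dependent variable", with "intervention group as the independent factor of interest, and baseline value of outcome as a covariate". In the nocturia model that covariate is baseline nocturia. For Aim 2, "researchers will add FUSP change and NPI change (both individually and together) as additional independent variables to the Aim 1 ANOVA models"; the ANOVA models named there are the ANCOVA models of Aim 1. The reading rule is: "Any subsequent reduction in intervention effect will be interpreted as supporting the Aim 2 mediation hypotheses".

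A mediator baseline could enter the nocturia model by one route only, after a baseline comparison between the groups: "Any significant differences will be used as additional covariates in sensitivity analyses".

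Three further points set the context. The Study Overview lists all three outcome measures as changes. It describes the mechanistic aim as "exploring the potential mechanisms by which BBTI impacts nocturia". The SAP says that, as suits a pilot, "researchers will focus interpretations on magnitudes of effects from standard statistical methods rather than their p-values".

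**The concern.** Aim 1 adjusts each outcome for its own baseline, so it is striking that the Aim 2 nocturia model takes in mediator change without the mediator's baseline. A change score entered alone carries a restriction: baseline and follow-up mediator must have equal and opposite coefficients. The plan neither states nor tests this.

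The route through baseline differences does not test it either. With two independent tests at an assumed 0.05, chance would flag FUSP or NPi in 1 - 0.95² = 9.75% of trials. Balance between arms also says nothing about how the baseline mediator relates to nocturia within arms.

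If the restriction is false, the group effect falls too little when the mediator is added, and mediation looks smaller than it is. Because the plan interprets magnitudes, and the data are to inform a larger trial, an understated mediated share could mislead. The baselines are already collected, so adding them looks like a free correction.

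**Working it through.** **No plan figure to reproduce.** The documents give 60 participants at 1:1, but no SDs, correlations or effect sizes for Aim 2. All inputs below are assumptions in SD units.

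**The restriction.** Let Y be nocturia, M a mediator, A the group, and 0 and 1 the two visits.

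- Planned: ΔY = β0 + c'A + βY·Y0 + b(M1 - M0)
- Adjusted: the same plus γ·M0

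The planned model sets γ = 0. If only change acts, γ = 0 is true and both models are right. Otherwise the large-sample planned coefficient is b multiplied by

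k = Cov(X, ΔM | A, Y0) / Var(ΔM | A, Y0),

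where X is the function of M that drives Y1.

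**Inputs.** Effect of group on mediator a = 0.6; b = -0.5; direct effect 0. True indirect effect: 0.6 × (-0.5) = -0.30. Let ρ be the test-retest correlation of M and r the baseline correlation of M and Y.

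- Only follow-up level matters (X = M1), r = 0: k = (1 - ρ)/(2 - 2ρ) = 0.5; indirect effect -0.30 × 0.5 = -0.15.
- Same, r = -0.7, ρ = 0.6: Var(M0|Y0) = 1 - 0.49 = 0.51; Cov(M0,M1|Y0) = 0.6 × 0.51 = 0.306; Var(M1|Y0) = 0.36 × 0.51 + 0.64 = 0.8236. So k = (0.8236 - 0.306)/(0.8236 + 0.51 - 0.612) = 0.5176/0.7216 = 0.717; indirect effect about -0.22.
- Mixed (X = M1 - 0.5·M0), r = 0: k = 1.5(1 - ρ)/(2 - 2ρ) = 0.75; indirect effect -0.225.
- Only change matters (X = ΔM): k = 1; indirect effect -0.30.

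The large-sample shift is therefore real under some mechanisms and absent under another.

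**Total error at the planned size.** Trials of 60 were simulated with ρ = 0.6 (except under a stable factor) and r = 0, -0.5 and -0.7 where r is a free input. Mediation was read as the plan reads it, as the fall in the group coefficient. For the adjusted model, the total effect came from a model with the same baseline covariates. There was no measurement error.

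| Mechanism | True | Large-sample, planned | Large-sample, adjusted | RMSE n=60, planned | RMSE n=60, adjusted |
|---|---|---|---|---|---|
| Follow-up level only | -0.30 | -0.15 to -0.22 | -0.30 | 0.161-0.180 (r = -0.5, 0); 0.143 (r = -0.7) | about 0.13 |
| Same level relation at both visits | -0.30 | -0.25 to -0.26 | -0.30 | 0.124 | 0.128 |
| Mixed level and change | -0.30 | -0.225 to -0.26 | -0.30 | 0.130-0.138 | 0.132-0.133 |
| Change only | -0.30 | -0.30 | -0.30 | 0.134-0.141 | 0.132-0.136 |
| Stable unmeasured factor, no mediation | 0 | 0.00 | -0.10 to -0.15 | 0.07-0.08 | 0.14-0.18 |
| Stable unmeasured factor, mediation | -0.30 | -0.22 to -0.25 | -0.40 to -0.45 | 0.15-0.16 | 0.21-0.24 |

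The adjusted model is clearly better in the first row, clearly worse in the last two, and about equal in the other three.

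**Shift against noise.** In the first three rows the false direct effect is 0.04 to 0.15. The sampling SD of the planned group term is 0.21-0.24 in the first and third rows and 0.17-0.18 in the second.

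**Would a second estimate reveal the problem?** On the plan's reading, the two estimates differ by 0.10 or more in 5-12% of trials when only change matters, where both models are right. With the same level relation at both visits, where the planned model loses about 15%, the figure is 13%. Comparing the models hardly separates these two situations. Large gaps are common when only follow-up level matters (33-73%) and with a stable factor (43-84%; both computed from the product of the two paths). Those two call for opposite conclusions about which model to believe.

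**The case for a change.** The strongest case for the concern is that the restriction is real, unstated and untested; that it affects magnitude, which the plan chooses to interpret; and that relaxing it costs one residual degree of freedom for one mediator (56 to 55) or two for both (55 to 53).

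Some results do favour adjustment. A separate set of inputs (a = 0.6, b = -0.4, direct effect -0.2, true share mediated 55%) gave a planned share of 29-36% when only follow-up level matters, and 16-28% when baseline level adds a further effect of half b. Power of the Sobel test when only follow-up level matters was 20-42% planned v 66-67% adjusted. The mediators come from a short diary ("Sleep/ bladder diary: Explain 3 day sleep and voiding diary instructions"). With an assumed error variance of 0.25 both models are biased, the planned one more so when only level matters: -0.09 to -0.13 v -0.22.

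The algebra stands, and so does the possibility of understated mediation. What does not follow is that the plan is wrong or that the alternative repairs it.

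- The 50% loss needs mediator and nocturia to be uncorrelated at baseline while the mediator drives nocturia afterwards. That sits badly with the Introduction, which treats nocturnal polyuria as a main contributor to nocturia.
- With a stable factor and no mediation, the adjusted model's Sobel test rejects in 5-17% of trials, against 1% for the planned model.
- In the scenarios with true mediation and neither measurement error nor a stable factor, the planned group effect falls in the right direction in about 97% or more of trials. Direction is all that the plan's rule uses; it nowhere claims partial or complete mediation.

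**Conclusion.** There is no defect to correct. The plan omits the mediator baselines from the Aim 2 nocturia models, but the choice is coherent: the outcomes are defined as changes, Aim 2 begins with correlations among changes, and the mediation models continue on that scale. Under a change-only mechanism the loss is zero. Under the level-based mechanisms examined it is about 13-50% of the indirect effect in large samples. At n=60 the error of the estimate improves clearly only when follow-up level alone matters, and it worsens with a stable shared factor. Two unranked estimates with no rule for choosing between them would correct no stated figure or result. Reasonable statisticians could report one model or both.

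The conclusion rests on assumed effect sizes and correlations, on single-mediator models (the joint FUSP and NPi model was not simulated), and, for the error comparison, on mediators measured without error. It also presumes post-intervention data in both arms, as the Study Overview describes. Aim 1 is unaffected.
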